**Data management and Statistical analysis:**

Data entry, data processing, and statistical analysis will be done using IBM Statistical

Software for Social Sciences (SPSS, Inc., Chicago, IL) version 20.0. Continuous variables (such as age, anthropometric measurements, laboratory values of assay) will be checked for normality using one-sample

Kolmogorov-Smirnoff test, and expressed as means  $\pm$  standard deviation or median  $\pm$  interquartile range (for data that are not normally distributed).

Categorical variables (such as race, socioeconomic characteristics) will be expressed as frequencies with accompanying percentages. Differences between groups will be compared using the Pearson's Chi-square test or Fisher's exact test for categorical variables. Odds ratio and the corresponding 95% confidence intervals (CI) will be presented. The student t test and ANOVA will be used to compare difference between groups for normally distributed continuous variables. Comparison of continuous variables that were not normally distributed will be done using non-parametric (Mann-Whitney U test or Kruskal-Wallis test) inferential statistical test.

Linear and logistic regression analysis (univariate and multivariate) will be performed to evaluate the relationship between dependent and independent variables. Test of statistical significance will be set at p-value less than 0.05.

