#### Secondary

2. To determine the distribution of phenotypes among women diagnosed with PCOS in the above objective overall and by ethnicity. PCOS sub phenotypes are as follows: Phenotype A – clinical and/or biochemical hyperandrogenism (HA) and oligi-/anovulation (OA), and polycystic ovarian morphology (PCOM); B – HA and OA; C – HA and PCOM; and D – OA and PCOM;
3. To determine the risks for, metabolic syndrome, depression, obstructive sleep apnea symptoms, fibroids, and general health issues for PCOS women versus women without PCOS in the age groups 18 – 45 years.
4. To determine the genotype of PCOS in Trinidad.

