#### Strategies for Sampling, Recruitment and Retention

Participants will be sampled proportionally from all 8 zones as shown above in Trinidad. Approximately 124 women in the reproductive age (18 – 45 years old) will be randomly sampled from each zone. Houses will be numbered and random numbers of these houses will be generated using random number calculator. In each sampled house, females would be prescreened and those that satisfy our inclusion criteria would be selected. Telephone numbers of participants will be obtained and follow-up calls made.

Sample size calculations were based on the following formula (32):

$$n = [(Z_{1-\alpha})^2(P(1 - P)/D^2)]$$

where n = individual sample size,  $Z_{1-\alpha} = 1.96$  (when  $\alpha = 0.05$ ), P = assumed prevalence, and D = absolute error.

Sampling units are defined as individual unselected women between the ages of 18 and 45 years, identified in the community. We target power analysis on women who do not use hormonal contraception. We assume a conservative response rate of 50% of sampled women. This response rate includes the following parameters:

use of hormone/contraceptive use (15%), excluded due to hysterectomy or ovariectomy (3%), excluded due to pregnancy (2%), refusal to participate (20%), and study drop-out/lost to follow-up (10%).

A conservative prevalence estimate for PCOS based on a review of nine studies conducted in the general population using the Rotterdam 2003 definition is 13.4% (4, 5, 33-39). Using the above formula, a sample size of 495 individuals will be required to determine the prevalence with an absolute error of  $\pm 3\%$ . Assuming a 50% enrollment rate, 990 women would need to be approached for study inclusion.

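### The pooled-variance t test and ANOVA are planned for PCOS and non-PCOS groups of probably very unequal size; Welch's versions would keep the error rate at about 5% whichever group is more variable

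*Combined protocol and SAP*

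**What the plan says.** The section on data management and statistical analysis begins with a normality check: "Continuous variables (such as age, anthropometric measurements, laboratory values of assay) will be checked for normality using one-sample" Kolmogorov-Smirnov. Variables judged normal then follow this rule: "The student t test and ANOVA will be used to compare difference between groups for normally distributed continuous variables". The others go to Mann-Whitney or Kruskal-Wallis. The level is given as "Test of statistical significance will be set at p-value less than 0.05".

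The section does not say:
- whether the t test has the pooled or the unequal-variance form;
- whether equality of variances is examined;
- whether the normality test uses a mean and SD estimated from the same data, and with what correction;
- whether normality is judged in all women together or within each group.

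It speaks only of groups. The natural pair comes from the third objective in the list of aims, which concerns "general health issues for PCOS women versus women without PCOS in the age groups 18" to 45 years.

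**The concern.** Student's t test normally means the pooled-variance test. It tolerates unequal spread when the groups are of similar size, but not when one is much larger. The pooled variance is dominated by the larger group, while the uncertainty of the difference is dominated by the smaller one. If the smaller group is more variable, the standard error is too small and false positives rise. If it is less variable, the standard error is too large and real differences are missed.

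Unequal spread is plausible here. The PCOS group pools three phenotypes that include hyperandrogenism with one (D) that does not, which could widen the spread of androgens and of anything that tracks them.

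At stake are the p-values of the unadjusted comparisons of anthropometric and laboratory values, and of SF-12, Beck and Epworth scores if these are analysed as continuous.

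**Working it through.** **Inputs from the documents** (Strategies for Sampling, Recruitment and Retention)
- Prevalence: "using the Rotterdam 2003 definition is 13.4" per cent.
- Precision and size: "a sample size of 495 individuals will be required to determine the prevalence with an absolute error of" 3 percentage points.
- Approached: "Assuming a 50% enrollment rate, 990 women would need to be approached for study inclusion".
- Losses: the 50% already contains "refusal to participate (20%), and study drop-out/lost to follow-up (10" per cent), so 495 needs no further reduction.
- Level: 5%, taken as two-sided, in line with the 1.96 in the sample size formula.

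**Assumed:** the ratio r = PCOS SD / non-PCOS SD (the documents give no SDs), and normal data.

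**Step 1. The plan's own figure.** n = 1.96² × 0.134 × 0.866 / 0.03² = 495.3, so 495 is reproduced; 495 / 0.5 = 990.

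**Step 2. Group sizes.** 495 × 0.134 = 66.3 and 495 × 0.866 = 428.7, so about 66 and 429. The plan does not state this split; it follows if the enrolled women have the assumed prevalence.

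**Step 3. Error rate of the pooled test.** With the non-PCOS SD set to 1:
- true variance of the difference: V = r²/66 + 1/429
- variance the test uses: E = [(65r² + 428)/493] × (1/66 + 1/429)
- false-positive rate ≈ 2 × [1 − Φ(1.96 × √(E/V))]

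Example, r = 1.5: V = 2.25/66 + 1/429 = 0.03642. E = (574.25/493) × 0.01748 = 0.02036. √(E/V) = 0.748, and 1.96 × 0.748 = 1.466. The rate is 14.3%.

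| r | Pooled, formula | Pooled, simulated | Welch, simulated |
|---|---|---|---|
| 0.5 | 0.2% | 0.2% | 5.1% |
| 0.8 | 2.1% | 2.2% | 5.1% |
| 1 | 5.0% | 4.9% | 4.9% |
| 1.1 | 6.8% | 6.8% | 5.1% |
| 1.25 | 9.6% | 9.5% | 4.9% |
| 1.5 | 14.3% | 14.2% | 5.0% |
| 2 | 22.2% | 22.0% | 5.1% |

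The simulations used 40,000 data sets per row. A separate simulation gave 9.3%, 14.6% and 22.0% for r = 1.25, 1.5 and 2, and 2.2% and 0.3% for r = 0.8 and 0.5.

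**Step 4. Dependence on the split** (same formula, total 495)

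| PCOS v non-PCOS | r = 1.25 | r = 1.5 | r = 2 |
|---|---|---|---|
| 66 v 429 | 9.6% | 14.3% | 22.2% |
| 100 v 395 | 8.6% | 12.1% | 17.8% |
| 150 v 345 | 7.2% | 9.3% | 12.4% |
| 250 v 245 | 4.9% | 4.9% | 4.9% |
| 300 v 195 | 4.0% | 3.3% | 2.6% |

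Simulation at 150 v 345 gave 6.9% to 12.9%.

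**Step 5. Does the normality check help?** The full rule was simulated at 66 v 429 (Kolmogorov-Smirnov on all women together, then t or Mann-Whitney; 10,000 data sets per ratio). It gave 5.3%, 10.3%, 14.6% and 22.6% for r = 1, 1.25, 1.5 and 2. The check neither causes the inflation nor removes it. With mean and SD estimated from the data and no correction, its own actual level is 0.00% at n = 66 and 0.03% at n = 495, against 5%.

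**The case against.** Much of the case on the other side stands.

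- **Direction and size are not in the documents.** With no SDs given, a reader might infer that the plan as written doubles to quadruples false positives. The documents do not support that. It needs the PCOS group to be the more variable, by a factor of about 1.25 to 2; the opposite pattern makes the test conservative.
- **The split may not be 66 against 429.** The 13.4% is a general-population figure, whereas the inclusion criteria require at least one PCOS-type feature. The PCOS share among enrolled women could well be higher. Step 4 shows the inflation shrinking, vanishing near 1:1 and reversing if PCOS is the majority.
- **The normality test is not the source of error.** A reader might infer that a badly calibrated gate corrupts the p-values. With equal SDs the two-stage rule runs at 5.3%. Nor does the gate always miss skewness. A log-normal with skewness about 1.3 is detected in only about 6-8% of samples at n = 66, but in about 99% if all 495 women are checked together, and the plan does not say which applies. With identical log-normal distributions in both groups (log-SD 0.4 to 0.8), Student's t at 66 v 429 held 4.8-5.1%, and Welch on the unlogged values ran slightly high at 5.5-6.3%. That is a reason to use the log scale for skewed assays, not to keep the pooled test.
- **Androgens are a poor example.** They help define PCOS, so equal means are hardly a live null hypothesis. The point bears more on the other continuous measures.
- **Reach is limited.** The primary outcome is a prevalence, and the named comparisons (metabolic syndrome, depression, sleep apnea symptoms, fibroids, general health) are adjusted odds ratios. No t-test comparison is singled out as confirmatory.

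The core remains: the plan names a test whose validity depends on a split and on spreads that are not known in advance, when a test that depends on neither is available.

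**Conclusion.** The point holds as a low-severity improvement. At the planning split of 66 v 429, the pooled test's false-positive rate is about 9-10%, 14-15% and 22% for assumed PCOS SDs 1.25, 1.5 and 2 times larger. It is about 2% and 0.2-0.3% for SDs 0.8 and 0.5 times as large. At 150 v 345 the inflated rates are about 7-13%, and near 1:1 there is no problem. Welch's test stays near 5% in these cases.

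This rests on reading Student's t test as the pooled form (usual, but not spelled out), on PCOS versus non-PCOS being the groups meant, on normal data, and on assumed SD ratios. No figures were worked out for ANOVA; the same mechanism applies there. It would be wrong to conclude that the study's main results are affected: neither the prevalence estimate nor the adjusted odds ratios use this test.

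**What to change.** In the statistical analysis section:
- replace Student's t test and ANOVA with Welch's t test and Welch ANOVA for unadjusted comparisons of continuous variables;
- do not let the uncorrected Kolmogorov-Smirnov result choose the test;
- name in advance the assays known to be skewed and compare them on the log scale.

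Medians and quartiles can stay for description. The cost is a change of wording, with standard software options and no extra women or data. The downside is slightly wider intervals for some comparisons.

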#### **Ethical considerations:**

This study will be conducted according to the ethical guidelines and principles of The International Declaration of Helsinki, the Guidelines for Good Clinical Practice and the National Code of Health Research Ethics (NCHRE). The Ethical Committee for The University of the West Indies will issue approval. All researchers involved in this research project have received training in Responsible Conduct of Research.

No participant recruitment will commence until the approval is received. Written informed consent will be obtained from all participants before recruitment. Material transfer agreement will be signed with collaborators. In designing this study, the following ethical issues were put into consideration.

#### **Consent to participate and withdraw from study:**

The purpose of the study will be explained to all the potential participants. An informed written consent will be obtained from each study participant before recruitment into the study. Study participants will be informed of their freedom to withdraw or refuse to take part in the study without prejudice to their usually expected standard of care. No financial or material incentive will be given to participants.

An investigator may terminate a study's participant in the study if:

1. Any medical condition, event or situation arises or is recognized such that continued participation in the study would not be in the best interest of the subject.
2. The subject is found to meet an exclusion criterion (either newly developed or not previously recognized) that precludes further study participation.

#### **Handling of subject withdrawals:**

When a subject chooses to withdraw, stating so directly or passively (i.e., does not return as scheduled) an attempt will be made to reach that individual in follow-up to ascertain that she is not suffering an untoward event that required evaluation or follow-up. Whatever data/tissue has collected until the time the subject withdraws will be available for analysis, unless the subject specifically states that such data/tissue specimens should be discarded and not used further, in which case the samples will be discarded and the data deleted from the database. Withdrawn subjects will not be replaced.

**Confidentiality of data:**

All information about the participants will be obtained using anonymous questionnaires and shall be kept strictly confidential. The participants will be assured that their identity will be kept in confidence by the investigators and that the results obtained will be presented in aggregate manner.

**Beneficence to participants:**

No participant in this study will be made to pay for any of the procedures. The study participants will be informed of the OGTT results and pelvic ultrasonographic findings. All study participants with abnormal findings will be notified of the results of their evaluation, and those with abnormal physical, historical or biochemical findings will be encouraged to undergo further investigation or treatment.

**Non Maleficence to the participants:**

All precautions will be taken to reduce the discomfort that may result from the venipuncture or during ultrasonography.

**Job description**

The physicians and nurses will be responsible for identification of potential study participant, education and counselling, and filling the questionnaires. The medically trained Research Assistants will be responsible for the anthropometric measurements and initial physical examination. The physicians will be responsible for the physical examination. The Gynecologist will be responsible for the pelvic ultrasonography. The Research Technician and Assistant will be responsible for the blood sample collection and processing under the supervision of the pathologist.

